DL=dose level; Q3W=every 3 weeks.

Infusion of tusamitamab rfvansine will be administered at least 1 hour after the end of ramucirumab infusion. For patients with a BSA >2.20 m², the tusamitamab rfvansine dose will be calculated based on a BSA of 2.20 m².

Figure 2 - Decision tree for triplet cohort for tusamitamab ravtansine

* Note: In case of 2 or more DLTs at DL - 1, the cohort may be stopped or the dosage reconsidered.

Abbreviations: DL -1=dose level -1 (120 mg/m²); DLT=dose-limiting toxicity; RP2D=recommended dose.

The study cut-off for the secondary ORR endpoint analysis of triplet cohort corresponds to the date on which all evaluable treated patients have had at least 2 post baseline tumor assessments, experienced confirmed objective response, or have discontinued the study for any reason. This study cut-off will occur approximately 4.5 months after the date of the first IMP administration of the last participant: 3 months for 2 tumor assessments and 1.5 months if a confirmation of response is needed.

Disclosure Statement: This is a single-arm, 2 cohorts, open-label, treatment study with no masking in patients with previously treated metastatic NSQ NSCLC.

Number of participants:

In the doublet cohort, approximately 225 participants will be prescreened to achieve up to approximately 36 treated participants, based on an estimated CEACAM5 prescreening failure rate of 80% and an estimated study screen-failure rate of 20%.

In the triplet cohort, approximately 74 participants will be prescreened to achieve up to approximately 12 DLT evaluable participants, based on the doublet cohort CEACAM5 prescreening failure rate of 79% and an estimated study screen-failure rate of 23%.

Intervention groups and duration:

The duration of the study for a participant will include:

- **Screening period:** up to 28 days.
- **Treatment period:** once successfully screened, enrolled participants may receive study intervention until disease progression, unacceptable AE, or the participant's or investigator's decision to stop the treatment. Each cycle of treatment will have a duration of 2 weeks in the doublet cohort and 3 weeks in triplet cohort. After discontinuing study intervention, participants will return to the study site approximately 30 days after the last investigational medicinal product (IMP) administration or before the participant receives another anti-cancer therapy, whichever is earlier, for end-of-treatment assessments.

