- q Concomitant medication will be recorded in the eCRF from 28 days prior to the first study intervention administration, before every cycle during the study treatment period, and for up to 30 days after the final dose of study intervention. Once the participant has withdrawn from study treatment, concomitant medication should only be recorded if used to treat new or unresolved study treatment-related adverse events.
- r Tumor assessment will be made at every 6 weeks interval (± 7 days window) during the study treatment period until radiological disease progression; initiation of further anti-cancer therapy; death; or study cut-off of the secondary ORR endpoint of the triplet cohort. The scheduled tumor assessment time point will not be modified in case of a cycle delay.
- s CEA samples should be collected before IMP infusion.

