After the EOT visit, the **Follow-up (FU) visit** will be performed at 90 (± 7) days after the last infusion. During the FU visit, the participants will be monitored for all ongoing related AEs and all SAEs and AESIs, regardless of relationship until resolution or stabilization (ie, an event ongoing without any change for at least 3 months). All new related AEs, SAEs, or AESIs will be followed until resolution or stabilization. If ongoing IMP-related AEs and all SAEs/AESIs are resolved or stabilized, no further safety follow-up visit will be needed; if not resolved or stabilized, an on-site follow-up visit will be performed every 12 weeks (± 7 days) until resolution or stabilization.

For the doublet cohort, a participant who stopped treatment for a reason other than PD, follow-up visits will be performed every 12 weeks (± 7 days) after the last tumor assessment until documented radiological disease progression, start of a new anticancer therapy, death, study cut-off date of the secondary ORR endpoint of the triplet cohort, or withdrawal of participant's consent (whichever comes first).

The study cut-off for the primary ORR endpoint analysis corresponds to the date on which all evaluable treated patients have had at least 2 postbaseline tumor assessments, experienced confirmed objective response, or have discontinued the study for any reason; the study cut-off can be up to approximately 6 months (4 months for 2 assessments, with an additional 2 months if confirmation of a response is needed) from the date the last participant's first administration.

After the study cut-off date for the primary ORR analysis, if clinical benefit is observed, a patient still receiving study treatment can continue study treatment until PD, unacceptable toxicity, or withdrawal of participant's consent, and will continue to undergo all assessments as per the study flow chart.

Triplet cohort:

Participants will be treated with tusamitamab ravidansine and ramucirumab and pembrolizumab to assess the tolerability of the combination to be used in the subsequent studies. The first 3 participants will receive ramucirumab at 10 mg/kg followed by tusamitamab ravidansine at 150 mg/m² and pembrolizumab at 200 mg every 3 weeks (Q3W). Administration of tusamitamab ravidansine will begin at least 1 hour after completion of ramucirumab infusion.

DLT definition is reported in [Table 5](#).

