8.1 EFFICACY ASSESSMENTS

The assessment of antitumor activity of tusamitamab ravtansine combined with ramucirumab in doublet cohort is the primary efficacy objective.

All participants treated must have at least one measurable lesion as per RECIST v1.1 for inclusion based on tumor assessment defined in the SOA, [Section 1.3](#).

For the doublet cohort: Tumor assessment will be made every 8 weeks (± 7 days window), and a scheduled assessment time point will not be modified in case of a cycle delay. Thoracic-abdominal-pelvic CT-scan or MRI and any other examinations as clinically indicated will be performed to assess disease status at baseline; then every 8 weeks during the study treatment period until radiological disease progression, initiation of further anticancer therapy, death, or study cut-off of the secondary ORR endpoint of the triplet cohort, whichever comes first; and at the end of study treatment, except if already done at last cycle. Confirmatory radiological evaluation will be performed at least 4 weeks after initial documentation of response. After IMP discontinuation, tumor assessment should be performed at EOT for patients without imaging performed within past 4 weeks, and every 12 weeks (± 7 days) after the last tumor assessment until

disease progression or initiation of a new anticancer treatment, death, or the study cut-off date of the secondary ORR endpoint of the triplet cohort, whichever comes first.

For the triplet cohort: Tumor assessment will be made every 6 weeks (± 7 days window), and a scheduled assessment time point will not be modified in case of a cycle delay.

Thoracic-abdominal-pelvic CT-scan or MRI and any other examinations as clinically indicated will be performed to assess disease status at baseline; then every 6 weeks during the study treatment period until IMP discontinuation; and at the end of study treatment, except if already done at last cycle. Confirmatory radiological evaluation will be performed at least 4 weeks after initial documentation of response. After IMP discontinuation, tumor assessment should be performed at EOT for patients without imaging performed within past 4 weeks.

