#### **4.3.2.2 Confirmed objective response**

The primary efficacy analysis is based on the primary estimand 2 introduced in Section 1.2.1. It is defined according to the following attributes:

- The endpoint is confirmed objective response (confirmed CR or PR as BOR) as per RECIST 1.1.
- The treatment condition of interest is tusamitamab ravtansine in combination with ramucirumab.
- The analysis population is the subgroup of participants from the all-treated population (defined in [Section 3](#)) treated at the RP2D (ie, excluding participants treated at the starting dose if this differs from the RP2D).
- Intercurrent events:
  - The study intervention discontinuation intercurrent event will be handled with the treatment policy strategy. Confirmed objective response will be assessed based on tumor assessments regardless of study intervention discontinuation.
  - The further anticancer therapy (including further systemic anticancer therapies) intercurrent event will be handled with the “while not initiating further anticancer therapy” strategy. Confirmed objective response will be assessed based on tumor assessments done up to the time of initiation of further anticancer therapy.
- The population-level summary will include the ORR, defined as the rate of participants with confirmed objective response, and two-sided 95% confidence interval using the Clopper-Pearson method.

In the absence of confirmed objective response before the analysis cut-off date (taking into account the intercurrent event handling strategies), participants will be considered as non-responders, whatever the reason (including participants with non-evaluable best overall response).

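### The ORR cut-off is met at two scans even if the second shows an unconfirmed response, while the stated timing reserves further time for confirmation

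*Protocol*

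**What the plan says.** **Triplet** (Protocol 1.1 Synopsis, repeated in 4.1 and 7). The cut-off for the secondary ORR analysis is the date when "all evaluable treated patients have had at least 2 post baseline tumor assessments, experienced confirmed objective response, or have discontinued the study". The next sentence gives the timing: "This study cut-off will occur approximately 4.5 months after the date of the first IMP administration of the last participant", made up of "3 months for 2 tumor assessments and 1.5 months if a confirmation of response is needed".

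**Doublet** (Protocol 4.1 and 7; SAP 4.1 and 4.9). The primary ORR has the same three-part rule. Its timing is 4 months for two assessments, "with an additional 2 months if confirmation of a response is needed". Three of these places give 6 months as an upper limit; SAP 4.9 gives it as the approximate date.

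**Confirmation.** Protocol 8.1 states: "Confirmatory radiological evaluation will be performed at least 4 weeks after initial documentation of response". Protocol 9.4.1.1 counts only confirmed responses in the ORR numerator, over everyone in the analysis population. SAP 4.3.2.2, for the doublet, classes a participant as a non-responder "In the absence of confirmed objective response before the analysis cut-off date".

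**End of scanning.** In the triplet flow chart (1.3.2, footnote r), on-treatment scans run until progression, new therapy, death, "or study cut-off of the secondary ORR endpoint of the triplet cohort". Protocol 8.1 instead continues triplet scans until IMP discontinuation and names no cut-off.

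**The concern.** The rule and its timing sentence describe different dates. Two scans satisfy the rule whatever they show, so it never waits for a pending confirmation. The timing sentence adds time for exactly that purpose.

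ORR counts confirmed responses only. If the cut-off is declared when the last participant has had scan 2, a response first seen at that scan cannot yet be confirmed, and the participant stays in the denominator without counting in the numerator. The error can only lower ORR. The doublet ORR is the primary efficacy endpoint; the triplet ORR is secondary, but its denominator is so small that one participant matters.

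**Working it through.** **Inputs**
- Triplet scan interval, Protocol 1.3.2 footnote r: "Tumor assessment will be made at every 6 weeks interval (± 7 days window").
- Doublet scan interval: 8 weeks, same window (1.3.1 footnote r).
- Minimum gap to confirmation: 4 weeks (8.1).
- Stated cut-offs: 3 + 1.5 = 4.5 months (triplet); 4 + 2 = 6 months (doublet).
- Size: 30 evaluable in the doublet (9.2.2). The triplet plans 6 to 12 DLT-evaluable participants (9.2.3), but 9.4.1 restricts efficacy to the recommended dose and 12 arises only after de-escalation, so about 6.
- One calendar month = 365.25 / 12 / 7 = 4.348 weeks.

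**1. Reproduce the stated timing.** In four-week months:
- Triplet: 2 × 6 = 12 weeks = 3.0; plus 6 weeks = 1.5; total 18 weeks = 4.5.
- Doublet: 2 × 8 = 16 weeks = 4.0; plus 8 weeks = 2.0; total 24 weeks = 6.0.

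Both figures come out exactly, but only with a third scan included.

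**2. Apply the rule as worded, and find the earliest confirmation.**

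| | Trigger met (scan 2) | Earliest confirmation (+4 weeks) | Scheduled scan 3 | Stated cut-off |
|---|---|---|---|---|
| Triplet | week 12 (2.76 months) | week 16 (3.68) | week 18 (4.14) | 4.5 months = 19.6 weeks |
| Doublet | week 16 (3.68 months) | week 20 (4.60) | week 24 (5.52) | 6 months = 26.1 weeks |

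The literal trigger precedes the earliest possible confirmation of a scan-2 response by 4 weeks. The stated cut-off comes after scan 3.

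**3. Check whether the second limb rescues the rule.** A confirmed response needs two post-baseline scans at least 4 weeks apart. Anyone who has one already satisfies the two-scan limb, so the confirmed-response limb adds nothing.

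**4. Who is exposed.** A participant first dosed at least one scan interval before the last participant (6 weeks triplet, 8 weeks doublet) has reached scan 3 by the trigger date. Exposure to an unconfirmed scan-2 response is therefore confined mainly to those dosed within that interval. The documents give no timing for first responses. As an assumption, let each of k exposed participants have probability q of a first response at scan 2; the chance of at least one is 1 − (1 − q)^k:

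| q | k = 1 | k = 3 | k = 6 |
|---|---|---|---|
| 0.03 | 3.0% | 8.7% | 16.7% |
| 0.05 | 5.0% | 14.3% | 26.5% |
| 0.10 | 10.0% | 27.1% | 46.9% |

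**5. Effect of one lost responder** (Clopper-Pearson 95% intervals; the same calculation reproduces all five rows of Protocol Table 14):
- Doublet, 1/30 = 3.3 points. For example 9/30 = 30.0% (14.7 to 49.4) becomes 8/30 = 26.7% (12.3 to 45.9).
- Triplet, 1/6 = 16.7 points. For example 1/6 = 16.7% (0.4 to 64.1) becomes 0/6 = 0% (0 to 45.9).

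**The case against.** The strongest reply is that the definition should be read whole. The timing sentence sits beside the rule and plainly reserves time to confirm, so a sponsor following it would not cut off at week 12. This stands as evidence of intent: the defect is a drafting conflict, and bias arises only if the rule is applied literally. It does not remove the conflict, because no limb of the rule carries the condition.

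Several stronger readings are tempting and are not supported:

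- **That the doublet's primary ORR is permanently biased.** The SAP's non-responder rule runs to the analysis cut-off, which is the database extraction made after the study cut-off (SAP 4.1, 4.9), so a confirmatory scan in between counts. Doublet scans do not stop at the doublet cut-off; they run on to the triplet one (1.3.1 footnote r; 8.1). The final analysis updates all results (SAP 4.9).
- **That the triplet's confirmatory scan is cancelled.** Footnote r points that way, but 8.1 continues scans to IMP discontinuation and calls for confirmatory imaging. Section 7 keeps patients still on treatment under the flow chart's assessments, which leads back to footnote r. The documents leave the matter open.
- **That the SAP's non-responder rule governs the triplet.** SAP 1.1 says the SAP does not cover that cohort. The triplet effect rests on the confirmed-only numerator in Protocol 9.4.1.1.
- **That 12 is the triplet's ORR denominator.** Efficacy is summarised at one dose level, so a figure based on 12 describes no planned analysis.

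It is also fair that the effect needs a coincidence: late enrolment, first response at scan 2, literal use of the rule, and no confirming scan before extraction.

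**Conclusion.** The point holds as a conflict between the cut-off rule and its own stated timing, in both cohorts. Read literally, the rule can fire at about week 12 (triplet) or week 16 (doublet), before a scan-2 response can be confirmed, and the resulting error in confirmed ORR is downward.

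In the doublet the size is 3.3 points per affected participant at N=30. It mainly concerns the first-step analysis and is recoverable through the later extraction and the final analysis. In the triplet it is 16.7 points per affected participant, assuming about 6 treated at the recommended dose. Recovery there is uncertain because footnote r and 8.1 disagree and no SAP covers the cohort.

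These figures assume scans on schedule and literal use of the rule. If the cut-off is held to the stated 4.5 or 6 months, a scan-2 response can be confirmed in time. No hypothesis test is affected, since none is planned. The wording should be corrected before the cut-off is applied; it does not invalidate the design.

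**What to change.** Wherever the rule appears (Protocol 1.1, 4.1 and 7; SAP 4.1 and 4.9), add one condition: any CR or PR first documented at or before the second post-baseline assessment must have had its confirmatory assessment, at least 4 weeks later as 8.1 already requires, unless the participant has progressed, died, started other anticancer therapy or discontinued the study.

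Tie the condition to the second scan, not to the most recent one. A condition on the most recent scan would roll forward: a first triplet response at week 18 would need confirmation at week 22 or later, beyond 19.6 weeks. As proposed, when a confirmation is pending the cut-off falls at about weeks 16 to 18 (triplet) or 20 to 24 (doublet). With the 7-day window, scan 3 is at latest 4.37 or 5.75 months, inside the announced 4.5 and 6 months. A response first seen at scan 3 may still be unconfirmed at the cut-off; that limit is already implicit in the stated timings.

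Separately, reconcile 1.3.2 footnote r, section 7 and 8.1 on whether triplet scans continue after the cut-off.

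The cost is one clause in two documents and a cut-off that may fall a few weeks later than the literal rule would give.

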1.2 SCHEMA

A graphical representation of study design is shown in Figure 3:

Figure 3 - 3a-3b-3c - Graphical description of study design

Doublet cohort:

Figure 3a:

[figure not shown]
[figure not shown]

[figure not shown]
Figure 3b:

Safety run-in Part 1:

[figure not shown]

Part 2:

Triplet cohort:

Figure 3c:

1.3 SCHEDULE OF ACTIVITIES (SOA)

1.3.1 Study flow chart - Doublet cohort

Procedure	Pre-screening ^a	Screening ^b	Treatment cycle 1		Treatment cycle 2 +		End of treatment	90 (± 7) Days (3 month) Follow-up ^d	Notes*
Day		Days to first infusion	D1		14 (± 2) days from previous infusion		30 (± 5) days from last infusion		
			Pre-infusion ^c	EOI	Pre-infusion ^c	Every 8 weeks (± 7 days)			
CEACAM5 expression status ^a (archival or fresh tumor tissue) – central IHC/ prescreening Informed consent	X								
Informed Consent		X							
Inclusion/exclusion criteria		≤ 28	X						Section 5.1, 5.2
Demography, medical/surgical/disease/smoking history ^e		≤ 28							
NSCLC characteristics ^f	X	≤ 28							
Height		≤ 7							
Performance status (ECOG)		≤ 7	X		X		X	X	Section 8.2.1, 8.2.3
Physical examination, including vital signs, body weight ^g		≤ 7	X		X		X	X	Section 8.2.1
Hematology ^h		≤ 7	X		X		X		Section 8.2.5, 10.2 (Appendix 2)
Coagulation ⁱ		≤ 7	X		X		X		Section 10.2, (Appendix 2)
Clinical blood chemistry ^j		≤ 7	X		X		X		Section 8.2.5, 10.2 (Appendix 2)
Urinalysis ^k		≤ 7	X		X				Section 10.2, (Appendix 2)
HBsAg & HCV serology and HIV test (only if required at country level)		X							Section 10.8, (Appendix 8)

Procedure	Pre-screening ^a	Screening ^b	Treatment cycle 1		Treatment cycle 2 +		End of treatment	90 (± 7) Days (3 month) Follow-up ^d	Notes*
Day		Days to first infusion	D1		14 (± 2) days from previous infusion		30 (± 5) days from last infusion		
			Pre-infusion ^c	EOI	Pre-infusion ^c	Every 8 weeks (± 7 days)			
Urine or Serum pregnancy test ^l		≤ 7			X		X	X	Section 10.2 (Appendix 2) Section 10.5 (Appendix 5)
Left ventricular ejection fraction (MUGA/echocardiogram) ^m		≤ 28							Section 8.2.4.2
12-lead ECG ⁿ		≤ 7	X	X	X		X		Section 8.2.4.1
Specific ocular tests ^o		≤ 28					X		Section 8.2.2
Tusamitamab rvtansine/Ramucirumab administration			X		X				Section 6.1
AE assessment ^p	X		Continuously throughout the study period						Section 8.2, 8.3, 10.3 (Appendix 3)
Concomitant medication ^q		X	Continuously throughout the study period						Section 6.5
Tumor assessment – RECIST v1.1 - CT/MRI; relevant surrogate markers ^r		≤ 28				X	X	X	Section 8.1
Circulating CEA ^s	X	≤ 28				X	X	X	
IgG			X						
Record further anticancer therapy								X	
Tusamitamab rvtansine and ramucirumab PK			Refer to PK/ATA flowchart, Section 1.3.3						Section 8.5
Tusamitamab rvtansine Immunogenicity			Refer to PK/ATA flowchart, Section 1.3.3						Section 8.9

Abbreviations: AE=adverse event; AESI=AE of special interest; ALT (SGPT)=alanine aminotransferase; AST (SGOT)=aspartate aminotransferase; ATA=antitherapeutic antibody; CEA=carcinoembryonic antigen; CEACAM5=carcinoembryonic antigen-related cell adhesion molecule 5; CR=complete remission; CT=computed tomography; eCRF=electronic case report form; ECOG=Eastern Cooperative Oncology Group (performance status); ECG=electrocardiogram; EOI=end of infusion; HBsAg=hepatitis B virus surface antigen; HCV=hepatitis C virus; HIV=human immunodeficiency virus; IMP=investigational medicinal product; LVEF=left ventricular ejection fraction; MRI=magnetic resonance imaging; MUGA=multigated acquisition scan; NSCLC=non-small-cell lung cancer; PD=progressive disease; PK=pharmacokinetic; PR=partial response; RBC=red blood cells; RECIST=Response Evaluation Criteria in Solid Tumors; SAE=serious AE; SD=stable disease; WBC=white blood cells.

a Prescreening: a prescreening Informed Consent will be signed by the patient for CEACAM5 assay on archival or fresh tumor tissue and circulating CEA assay unless results are available from an assay for circulating CEA and from CEACAM5 testing for another study; in this case, an addendum to the informed consent will be sufficient.

- b Screening: Informed consent should be signed before any study specific procedures. It can be signed more than 28 days prior to initiation of therapy. Screening time indicates in which timeframe exams used to support eligibility have to be done prior to initiation of therapy. All the tests or procedures on D1 should be done at predose time unless otherwise stated. Assessments must be performed prior to first IMP administration: participants must have confirmed CEACAM5 expression as assessed centrally. Baseline evaluation should be completed within 1 week prior to initiation of therapy, except for tumor assessment, circulating CEA, echocardiography, and ocular tests that may be performed within 4 weeks prior to the first IMP administration. Results of these tests should be reviewed by the Investigator prior to initiation of therapy.
- c D1 pre-dose: Cycle 1 D1 refers to the day the participant receives the initial dose of IMP. D1 of Cycle 2 and of each subsequent cycle corresponds to D15 of the previous cycle. During treatment, D1 assessment can be done on the day of infusion (before infusion) or the day before. C1D1 hematology, blood chemistry, coagulation and urinalysis tests may be omitted if baseline test performed within 7 days are normal. If baseline tests are abnormal should be repeated within 2 days of first study intervention.
- d Follow-up visit: SAEs (regardless of relationship with study treatment) and IMP-related AEs ongoing at the end of study treatment, and any new IMP-related AE/SAE/AESI will be followed until resolution or stabilization (defined as an event ongoing without any change for at least 3 months). Date of disease progression and further anticancer treatment will be collected at the follow-up visit. Participants who stopped treatment before documented progressive disease (PD; ie, achieving stable disease [SD], or complete or partial response [CR or PR]) should undergo a tumor assessment and an on-site follow-up visit every 12 weeks (± 7 days) after the last tumor assessment until radiological disease progression, death, study cut-off date of the secondary ORR endpoint of the triplet cohort, initiation of further anti-cancer therapy, or withdrawal of participant's consent, whichever comes first. Participants with documented disease progression should attend an on-site follow-up visit 90 days after the last dose of study medication. If every ongoing related AE/SAE/AESI is resolved or stabilized, no further follow-up visit is needed.
- e Disease history includes previous antitumor therapy (type, start and end dates, reason for discontinuation and response to the therapy) and smoking history.
- f NSCLC characteristics will include histologic types, stage at diagnosis, disease extent at study entry, (collected at screening) and specific mutations including PD-1 expression status (to be collected only at prescreening).
- g Physical examination will include: vital signs (temperature, blood pressure, heart rate) and examination of major body systems. Signs and symptoms will be reported in the electronic case report form (eCRF) as AEs only if they are still present at the time of first IMP administration
- h Hematology: Hemoglobin, hematocrit, RBC, WBC with differential, platelet counts. These tests will be done before IMP administration at each cycle. If Grade 4 neutropenia, assess absolute neutrophil count (ANC) every 2-3 days until ANC $\geq 0.5 \times 10^9/L$. During first 2 cycles, hematology will be performed weekly.
- i Coagulation: International normalized ratio (INR), aPTT.
- j Clinical blood chemistry: Liver function tests: SGOT (AST), SGPT (ALT), total bilirubin, conjugated bilirubin, AP. Renal function tests: Urea (or BUN) & creatinine. Electrolytes: Sodium, potassium, calcium, glucose. Others: LDH, albumin and total proteins. During first cycle, liver function tests will be performed weekly. The liver function tests and renal function tests will be done before IMP administration at each cycle, unless clinically appropriate. In case of Grade ≥ 3 liver function abnormal tests, additional tests will be repeated every 2-3 days until recovery to baseline value.
- k Urinalysis tests on morning spot will be performed by dipstick at baseline, and at every treatment cycle. In case of proteinuria $\geq ++$ (dipstick), proteinuria quantification by proteinuria/24 h should be performed.
- l Serum pregnancy test: women of childbearing potential must have a negative serum pregnancy test result within 7 days prior to the initial dose of IMP. A pregnancy test (serum/urine) will be repeated every 4 weeks before IMP administration, and a serum test will be repeated at the End of Treatment evaluation (30 \pm 5 days after the last IMP administration), and at the Follow-up visit (90 \pm 7 days after last IMP dose).
- m Echocardiogram or MUGA scan: left ventricular ejection fraction (LVEF) will be evaluated during screening period, and whenever clinically indicated.
- n 12-lead ECG is required at baseline (In case the ECG performed less than 7 days before 1st IMP administration is considered as normal, there is no need to repeat it just before the 1st IMP) before starting the and after completing the first IMP administration (within 30 minutes after the end of tusamitamab ravtansine infusion). The ECG after the infusion at cycle1 should be performed at any case; before IMP administration at each cycle; and at the End of treatment evaluation, 22 to 30 days after last IMP administration.
- o Specific ocular tests will include assessment of ocular/visual symptoms and ocular exams including visual acuity, slit lamp under dilatation, and Schirmer's test at screening and whenever clinically indicated.
- p AE: For participant who was prescreened and had fresh biopsy, only the Adverse Events related to the fresh biopsy procedure itself should also be reported in eCRF as general requirement of AE/SAE with the reporting time frame interval of 1 month for the prescreening period after fresh biopsy.
- q Concomitant medication will be recorded in the eCRF from 28 days prior to the first study intervention administration, before every cycle during the study treatment period, and for up to 30 days after the final dose of study intervention. Once the participant has withdrawn from study treatment, concomitant medication should only be recorded if used to treat new or unresolved study treatment-related adverse events.
- r Tumor assessment will be made at every 8 weeks interval (± 7 days window) during the study treatment period until radiological disease progression; initiation of further anti-cancer therapy; death; or study cut-off of the secondary ORR endpoint of the triplet cohort. The scheduled tumor assessment time point will not be modified in case of a cycle delay.
- s CEA samples should be collected before IMP infusion.

